9 STATISTICAL CONSIDERATIONS

9.1 General Design Issues

Overall design (from Precis section): 50 Younger Adults will be randomly assigned to three between-subjects tDCS conditions (left prefrontal, sham, left parietal control, total YA n=150) and 50 cognitively normal older adults will be randomly assigned to two between-subject tDCS conditions (left prefrontal, sham, total OA n=100). Each participant will complete 3 sessions: orientation/baseline (no tDCS, time varies), AM tDCS, PM tDCS (counterbalancing the order of the AM and PM sessions). Primary outcome measures will be cognitive task performance (episodic recollection accuracy primary, working memory accuracy secondary) as a function of 3 key factors (age group, tDCS condition, and time-of-day) and their interaction,

-
-

and also as a function of secondary factors obtained from actigraphy sleep data, sleep diary/log data, and the Morningness-Eveningness Questionnaire (aka the Owl-Lark assessment).

Rationale for within-subjects AM and PM testing: Each participant will take both an AM and a PM testing session. Within-subjects designs are generally preferred over between-subject designs, because they reduce the impact of individual variability on performance that is unrelated to the AM/PM manipulation, thereby increasing the likelihood of detecting AM/PM effects. However, within-subject designs introduce the possibility of practice effects across sessions, but we will control for such order effects by counterbalancing the order of the AM and PM sessions across participants in each arm. Moreover, collecting a no-tDCS cognitive baseline for all participants (during the first session) will give all participants familiarity and practice with the cognitive tasks, thereby reducing the impact of such practice effects on the subsequent AM and PM tDCS/sham testing sessions.

Rationale for between-subjects tDCS/Sham design: Our previous tDCS work suggests that, on average, participants in stimulation and sham conditions do report different kinds of sensations. To avoid cross-session learning effects, which would invalidate the sham condition, the experiments we propose here will manipulate tDCS between-subjects: Each participant will participate in an AM (8 or 9 AM) and PM (3 or 4 PM) testing session (within-subjects), and will be randomly assigned to the same tDCS condition in each session (left dlPFC or sham in older adults; left dlPFC, left parietal, or sham in younger adults), thereby avoiding any cross-session learning effects from experiencing different tDCS conditions.

Rationale for cognitive baseline measures: All participants will take a baseline version of the cognitive tasks (without tDCS) during the orientation session, serving as a no-tDCS baseline (i.e., the “pre” condition in a pre-post design). These cognitive baseline measures are included to assess Aim 3: Determine the extent that a pre-post between-subjects tDCS design can improve the detection of stimulation effects, while also preserving the validity of the sham condition. Our initial analyses will focus on the between-subjects comparisons described above, but the statistical power of the between-subjects design to detect group differences (stimulation vs sham) is likely limited by individual variability in task performance (unrelated to stimulation). In an attempt to reduce the contribution of individual variability that is unrelated to stimulation, and thereby provide a more sensitive test of tDCS effects, we will conduct additional analyses that include the baseline performance for all participants as a covariate. The primary purpose of this measure is to assess the value of a pre-tDCS baseline in detecting tDCS effects, independent from potential time of day effects explored in the other aims. Thus, to minimize time constraints on the completion of the project, these orientation

○

○

session testing times (and baseline cognitive assessment) will be scheduled at the convenience of the participant and experimenter (i.e., baseline sessions can occur outside the AM and PM testing windows that are reserved for the tDCS/sham sessions).

2 Sample Size and Randomization

Power analysis: Our power analysis was based on our most recent and largest tDCS experiment with younger adults (Wong et al., in press, $n = 30$ per each between-subjects condition), which yielded a 12% difference in word test accuracy between sham (.23, $SD = .21$) and active tDCS (.35, $SD = .21$) in the 9 AM group, predicting that we would need 50 participants in each stimulation group in order to obtain a similar effect size (Cohen's $d = .57$, or a medium effect size) with 80% power at $p < .05$ (2 tailed, calculated with G-Power, v. 3.1.9.3). We therefore plan to test 50 younger adults and 50 older adults in each stimulation condition in order to detect effects of this magnitude. These sample sizes are considerably larger than most (if not all) of the between-subjects tDCS experiments on episodic memory published as of 2017. A sample size of 50 per condition also should yield sufficient power to detect the 2x2 interaction between brain stimulation (between-subjects) and time-of-day (within-subjects) in each age group, if we assume a similar effect size (partial eta squared = .06) for the interaction between time-of-day and stimulation we had obtained in younger adults in Wong et al. (in press), and also a .25 correlation between the repeated measures during AM and PM (80% power, alpha = .05).

9.2.1 Treatment Assignment Procedures

Younger adults will be randomly assigned to one of the three stimulation conditions (active frontal, active parietal, or sham: $\frac{1}{2}$ frontal, $\frac{1}{2}$ parietal), and older adults will be randomly assigned to one of the two stimulation conditions (active frontal, sham frontal).

[name] will keep the stimulation codes in a password protected Excel file, which will be shared with the DSMB. No other member of the research team will have access to the file.

Planned breaking of the stimulation codes will occur when the 50 planned participants have been tested in each arm of the study, or until the study is terminated in consultation with the DSMB.

The research team and DSMB will have full access to all other data collected throughout the study, in order to monitor the quality of the data and allow preliminary analyses of time-of-day effects, age group, and other variables (actigraphy, MEQ) on cognitive task performance, as well as the exploratory metamemory analysis of baseline cognitive task data (no tDCS).

-
-

9.3 Interim analyses and Stopping Rules

No interim analysis of tDCS/sham differences is planned. We plan a mid-point analysis of the baseline cognitive task data (see Exploratory Metamemory Analysis), but this will not involve breaking the blinding codes (baseline data are not associated with tDCS). The PI, in consultation with the DSMB, will temporarily suspend enrollment in the tDCS portions of the study if serious questions arise about efficacy, safety, or poor study performance (e.g., slow accrual, high losses-to-follow-up, and poor quality control). In this event, study enrollment will only recommence if DSMB and the PI agree that the issue(s) has been resolved, and make a designation that the study should (a) continue per protocol, (b) proceed with caution, (c) be further investigated, (d) be discontinued, or (e) be modified and then proceed.

Examples of findings that might trigger a safety review are the number of SAEs overall, the number of occurrences of a particular type of SAE, severe AEs/reactions, or increased frequency of events. Such findings are presented to the DSMB statistician to review the events by group to determine whether there are statistical as well as clinical concerns. The statistician reports their findings to a closed session of the DSMB or to the Safety Officer and/or NIA. The findings are used to determine what steps will be taken.

9.4 Outcomes

9.4.1 Primary outcome

Our primary dependent variable (DV) will be accuracy on the episodic memory and working memory tasks. These will be assessed in each of the 3 sessions (baseline no-tDCS, AM tDCS, PM tDCS). See Section 6: Study Procedures.

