50 Younger Adults will be randomly assigned to three between-subjects tDCS conditions (left prefrontal, sham, left parietal control, total YA n=150) and 50 cognitively normal older adults will be randomly assigned to two between-subject tDCS conditions (left prefrontal, sham, total OA n=100). Each participant will complete 3 sessions: orientation/baseline (no tDCS, time varies), AM tDCS, PM tDCS (counterbalancing the order of the AM and PM sessions). Primary outcome measures will be cognitive task performance (episodic recollection accuracy primary, working memory accuracy secondary) as a function of 3 key factors (age group, tDCS

○

○

condition, and time-of-day) and their interaction, and also as a function of secondary factors obtained from actigraphy sleep data, sleep diary/log data, and the Morningness-Eveningness Questionnaire (aka the Owl-Lark assessment).

Interventions and Duration

Morning testing sessions will be scheduled at 8 or 9 AM, afternoon testing sessions will be scheduled at 3 or 4 PM. These times were chosen to be similar to those we used in our preliminary work that demonstrated time-of-day effects on tDCS in younger adults (9 am vs 1 pm), except we have shifted the PM session to 3 or 4 PM to be more consistent with aging studies that have found AM and PM effects on episodic memory (May & Hasher, 2017; May et al., 1993; Intons-Peterson et al., 1998)

Active tDCS will involve 20 minutes of continuous electrical stimulation (2.0 milliamperes, mA). Sham tDCS will involve 1 minute of stimulation at the start of the 20 minute period (i.e., 30 s to gradually ramp up to 2.0 mA, and then 30 s to ramp down), and also 1 minute of stimulation at the end of the 20-minute period. As in our prior work, during stimulation participants are instructed to sit quietly while remaining awake in preparation for the upcoming memory test, but no further instructions are given.

Standard Anodal Procedure. The tDCS technique that we use, modeled after the most effective techniques found in the literature (e.g., Nitsche et al., 2008), and aimed at targeting left

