6.2 Description of Evaluations

Cognitive Tasks:

Episodic Memory Task. We will cross stimulus type (words vs. pictures) with a recollection difficulty manipulation (items studied once or twice), all within-subjects. For the picture study list, participants will study words followed by a corresponding picture of the object (half colored pictures, half line drawings). Participants will decide if each picture is high or low detail, thereby drawing attention to perceptual features. For the word study list, participants will see the names of common objects and will be prompted to make one of two semantic judgments (Made in a factory? Found in house?), thereby drawing attention to conceptual features. We will give two recollection tests alternating across mini-blocks to avoid order effects. On the picture test blocks, verbal labels for the studied pictures will be intermixed with non-studied items, and participants will make one of three response options (studied as color, line, or new) followed by a confidence judgment. The structure of the word test blocks will be similar, whereby participants will make one of three response options (studied with a factory judgment, a house judgment, or new) in addition to the confidence judgment. Within each test, the items studied in the two different picture formats (or semantic judgments) will be matched on familiarity, so that participants will need to use recollection to make source judgments. Although pictures are typically better recollected than words, we have found that discriminating between these two different picture formats (namely, color or line judgments during the picture test) and these two different semantic judgments (namely, factory or house judgments during the word test) can be matched on difficulty with the repetition manipulation (i.e., comparing once-presented pictures to repeated words, Sarfan et al., 2014), allowing us to disentangle material-specific effects from recollection difficulty. Our primary dependent variable (DV) will be source recollection accuracy (the proportion of studied items attributed to the correct source, minus the proportion of non-studied items incorrectly attributed to that source). During each experimental session, subjects will perform the episodic memory task followed by the working memory task (described below).

-
-

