Working Memory Task. Similar to the episodic memory task, the working memory task will involve a stimulus manipulation (verbal vs. visuospatial working memory) as well as a difficulty manipulation, all manipulated within-subjects and across mini-blocks to control for order effects. Specifically, we will use the N-back task with a verbal version (i.e., presenting the numbers 1-9 in a varied sequence) and a matched visuospatial version (i.e., presenting a colored square in one of 9 locations on a 3x3 grid in a varied sequence). Based on neuroimaging work, both tasks rely on bilateral PFC regions, but the former relies more heavily on left PFC, and the latter more heavily on the right PFC (for meta-analysis, see Owen et al., 2005). Difficulty will be manipulated by varying the N in the N-back task into “easy” and “difficult” versions for both younger and older adults (1 and 2 back for older adults, 2 and 3 back for younger adults). Our primary DV will be proportion of targets correctly identified minus the proportion of lures incorrectly endorsed.

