## Analysis Plan

### PRIMARY ANALYSES

Set 1 (1a, 1b, 1c). The first set of primary analyses will estimate the effect of tDCS to left dlPFC on cognitive performance and the extent to which different aspects of the cognitive task will be impacted. These analyses will be done separately for episodic and working memory.

1.a This analysis will be done on younger adults only. We shall use a linear mixed (i.e., random participant-level intercepts) model with memory performance (defined as memory accuracy computed by subtracting false alarms from target hits) as the dependent variable and stimulation condition (stimulation vs. sham), session Time of Day (AM, PM), and task manipulations (stimulus format and difficulty) as within-subjects predictors along with session order as a covariate (session 1, session 2). Interaction terms between stimulation condition and both task manipulation and time of day will be used to examine the impact of these variables on the stimulation effect.

1.b This analysis will use the same model as in 1a (above), but including data from both younger and older adults and a corresponding age-group factor in the model. Interaction terms between age group, stimulation condition, and time-of-day will be used to determine whether the overall stimulation effect is the same for older as for younger adults, and if not, whether the difference varies by time of day.

1.c This analysis will assess the impact of preferred time of day on tDCS effects, using wrist-worn (minimum 7-days, max 12-days) accelerometry to measure preferred time of day (i.e. “Owl” vs “Lark”), and validation using the subjective Morningness-Eveningness Questionnaire (MEQ). For this analysis, accelerometry-derived variables capturing preferred time of days (eg, including wake time, rise time and midpoint of sleep) will be added as covariates to the model in 1.b., and interactions between these, time of day and stimulation effects will be evaluated.

Set 2. The second set of primary analyses will focus on dlPFC vs parietal vs sham effects in younger adults only. For these analyses, similar models to those described above will be used (e.g., 1a, 1c, 2), except we will include 3 levels for tDCS (dlPFC, parietal, sham). We will test the relative fit of three models: (1) a model in which parietal has the same effect as sham, (2) a model in which parietal has the same effect as dlPFC, and (3) a model in which the effect of parietal differs from the other two conditions.

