### STATISTICAL SIGNIFICANCE

A two-sided p-value cutoff of 0.05 will be used for all null-hypothesis significance testing. In addition, point estimates for all first order and interaction effects will be reported, together with 95% confidence intervals. Between-individual contrasts (e.g., overall treatment effects) will be standardized (i.e., equivalent to Cohen’s d). Results of all analyses performed will be reported (not just those that meet the 0.05 cutoff). Since Hypotheses 1-4 are distinct, we shall not make any adjustment for multiple testing across the corresponding analyses. Within each analysis, we shall use a hierarchical approach in which we

begin with an overall test of the null hypothesis at the coarsest level, separately for episodic and working memory, and only if that is statistically significant will we conduct further testing among subgroups.

Although the primary analyses will utilize the frequentist approach to estimating and testing, we will complement this with a secondary Bayesian analysis using the same model. For parameters capturing treatment effects or between-group differences in treatment effects (i.e., interaction terms), we shall use a weakly informative prior (e.g.,  $\text{Normal}(0, 1-10)$ ). The primary value of this analysis will be to provide more interpretable (i.e., probability) statements about the magnitude of the effects of tDCS and about the amount of information contained in the data.

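### Protocol 9.4.1 makes both memory tasks primary, the Precis and 9.1 rank working memory secondary, and the supplied SAP text tests both at 0.05 without ranking

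*Protocol*

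**What the plan says.** **Outcome ranking in the protocol.** The Precis (Design and Outcomes) reads: "Primary outcome measures will be cognitive task performance (episodic recollection accuracy primary, working memory accuracy secondary". Section 9.1 repeats that sentence and says it comes from the Precis, so the two count as one source. Section 9.4.1, headed Primary outcome, gives no ranking: "Our primary dependent variable (DV) will be accuracy on the episodic memory and working memory tasks". It sends the reader to Section 6, where 6.2 says of the episodic task "Our primary dependent variable (DV) will be source recollection accuracy" and of the n-back task "Our primary DV will be proportion of targets correctly identified minus the proportion of lures incorrectly endorsed".

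**Testing in the SAP.** Of the Set 1 primary analyses it says: "These analyses will be done separately for episodic and working memory". On the cutoff: "A two-sided p-value cutoff of 0.05 will be used for all null-hypothesis significance testing". The hierarchical rule within each analysis is to "begin with an overall test of the null hypothesis at the coarsest level, separately for episodic and working memory", with subgroup tests following only if that test is significant. The SAP declines to adjust across Hypotheses 1-4. It also undertakes to report every analysis, with confidence intervals.

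**Other labels.** The SAP lists 1.c (chronotype) and Set 2 (parietal site) as primary analyses. The protocol's Objectives and section 1.2 class the sleep and chronotype questions and regional specificity as secondary.

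**The concern.** The section that formally defines the primary outcome disagrees with the design summary on whether working memory is primary or secondary. The supplied SAP text does not resolve this, because it treats the tasks in parallel at the full significance level.

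The protocol presents the study as a replication in a literature it calls mixed. A replication needs one outcome, fixed in advance, that decides whether it succeeded. As written, a result on either task can be presented as the primary one, at an error rate above the nominal 5%. The sample size is also justified on an episodic measure alone, so the ranking decides whether that justification covers the whole primary claim.

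**Working it through.** **1. Can the passages be reconciled?** The two statements in 6.2 can be read as naming the main score within each task. Section 9.4.1 cannot easily be read that way, since it is the outcome definition and names two tasks. The Precis sentence opens with a plural (primary outcome measures), but its parenthesis labels working memory secondary in so many words. The SAP gate runs from the overall test to subgroups within one task and does not link the two tasks.

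**2. The plan's own sample size.** Inputs from the power analysis in Protocol 9.2: word-test accuracy .23 (sham) and .35 (active) in the 9 AM group, SD .21, two-sided 0.05, 80% power, 50 per group.

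- d = (.35 − .23)/.21 = .571, reported as .57.
- Normal approximation: n = 2(1.960 + 0.842)²/.57² = 48.3, so 49 per group.
- Two-sample t test: 49.3, so 50 per group; power at 50 is 80.6%.

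The stated figure reproduces. No calculation is given for working memory.

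**3. Error rate if either task can carry the claim.** Take one overall stimulation contrast per task, each at two-sided 0.05, with no true effect on either.

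- Independent tests: 1 − (1 − .05)² = .0975.
- Correlated tests: 1 − P(|Z₁| < 1.96 and |Z₂| < 1.96), with Z₁ and Z₂ bivariate normal.

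The documents give no correlation between tasks, so a range is assumed. The simulations use 50 per arm. The younger-adult column (100,000 runs) corresponds to analysis 1a. The last column (50,000 runs, both age groups pooled and stratified by age) corresponds to 1b.

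| Assumed correlation | Closed form | Simulated, younger adults | Simulated, both age groups |
|---|---|---|---|
| 0 | .0975 | .096 | .099 |
| .25 | .0959 | .096 | .098 |
| .5 | .0907 | .090 | .091 |
| .75 | .0810 | .082 | .082 |

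With the episodic test alone, or with working memory tested only after the episodic test succeeds, the simulated rate is .049 to .051.

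**4. What each reading costs at d = .57.**

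- Episodic alone primary, or episodic first: the episodic test stays at 0.05, so 50 per group and 80.6% power stand.
- Both primary, success on either, alpha split to 0.025 each: the t test needs 59.8, so 60 per group. At 50 per group, power is 71.6%.

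**5. Not counted above.** Analyses 1a (younger adults) and 1b (both age groups) are both listed as primary. If the pooled contrast weights the age groups equally, their correlation is about √(1/2) = .71, and testing both on the episodic task alone gives about 8.3%. The baseline-adjusted repeats of each analysis are not counted either.

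**The case against.** The strongest reply is that this is one family of primary measures with episodic memory ranked first, and that 9.4.1 merely omits an order given earlier in the same chapter. Calling a working-memory result primary would contradict the Precis and 9.1, and the study is powered on an episodic measure only. This supports the episodic-first reading as the likely intent. It does not excuse the formal outcome section from stating it.

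A second reply points the other way: Aim 1 and the Primary Objective (section 1.1) mention the tasks without ranking them, so both may be intended as primary. An unranked mention does not override an explicit secondary label, but the authors should be free to choose this reading if they state its error control.

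Third, part of the SAP was not available for review, and Hypotheses 1-4 are not defined in the text that was. A ranking there cannot be excluded, so the SAP points apply to the supplied text only. The conflict between the Precis and 9.1 on one side and 9.4.1 on the other lies wholly within the protocol and does not depend on them.

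Fourth, full reporting with confidence intervals and gated subgroup tests already limit selective reporting. That is true, but they do not identify the result that decides the trial.

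Two cautions on the figures stand. No passage states an either-task success rule, so 9.8% is what the ambiguity permits and not a rate the plan adopts. The 80.6% is for word-test accuracy at 9 AM, not for an overall contrast across formats and sessions.

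**Conclusion.** The inconsistency is real and should be corrected. Section 9.4.1 conflicts with the Precis and 9.1 on the status of working memory, section 6.2 does not settle it, and the supplied SAP text neither ranks the tasks nor controls error across them.

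If either task may carry the claim, the false-positive chance is about 8% to 10% instead of 5%. This assumes one contrast per task, no true effect, and a correlation between the tests of 0 to .75. The planned sample size is not in error: it reproduces and stands if episodic memory is the sole or first-tested primary outcome.

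**What to change.** - In 9.4.1 and the SAP, name episodic source recollection accuracy as the single primary outcome, following the ranking in the Precis and 9.1. Make working memory secondary, or test it only after the episodic test succeeds.
- State which of 1a or 1b carries the primary claim. Without this, the 5% rate holds only for a single contrast.
- Label 1.c and Set 2 secondary, to agree with the protocol's Objectives and section 1.2.
- If both tasks are meant to be primary, correct the Precis and 9.1, say whether success requires either task or both, and state the error control. With an even alpha split, show the power: about 72% at 50 per group, or 60 per group for 80%.
- As a clarification only, replace the SAP's generic score (hits minus false alarms) with the two scores in 6.2: source recollection accuracy for the episodic task, and targets minus lures for n-back.

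Make these changes before the stimulation codes are broken. The cost of the preferred route is wording, with no change to data collection or sample size. The downside is that working-memory, chronotype and parietal results are reported as secondary. Under the fixed order, working memory can support a confirmatory claim only if the episodic test succeeds.
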